9 STATISTICAL CONSIDERATIONS

9.1 STATISTICAL HYPOTHESES

This is a feasibility trial to evaluate the ability to recruit and enroll health funds, collect endpoint data for primary and secondary outcome measures, and to collect process measures related to implementation of the intervention with three health funds. There is no formal hypothesis testing in this trial although we will calculate descriptive statistics at baseline and follow-up (6-months) to show change over time. The data will be used to compute statistical power for a future R01 if the current study is successful.

- Primary Endpoint(s):
 - a) We will calculate the Proportion of workers with opioid misuse, opioid use disorder and opioid overdose using administrative data. We will assess change of opioid misuse and opioid use disorder at 6 months following delivery of the intervention
 - b) We will calculate the proportion of workers with opioid misuse from worker surveys. We will assess change in opioid misuse at 6 months following delivery of the intervention.

- Secondary Endpoint(s):
 - a) We will calculate the proportion of workers with lost time using worker surveys. We will assess change in reported lost time at 6 months following delivery of the intervention.
 - b) We will calculate the proportion of workers reporting willingness to seek help for opioid abuse using worker surveys. We will assess change in reported willingness to seek help at 6 months following delivery of the intervention.

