9.4.2 ANALYSIS OF THE PRIMARY ENDPOINT(S)

- a) Administrative Claims
 - a. Outcome variables of interest
 - i. Opioid misuse- “Overlapping Rx” OR “Multiple Rx on same day, different provider”
 - ii. Chronic opioid use- more than 60 days supply in a 90 day window
 - iii. Opioid use disorder- ICD-10 T40* (Poisoning by, adverse effect of and underdosing of narcotics and psychodysleptics) &/Or ICD-10 F11* (opioid related disorders) &/or prescribed MAT (Drug name contained “methadone” or “buprenorphine”; picks up buprenorphine, suboxone, zubsolv, naltrexone, methadone, narcan, and vivitrol)
 - b. Compute statistics for baseline period (06/01/2019-05/31/2022) and follow-up (06/01/2022-05/31-2023)

- i. Categorical data will be presented as N (%), continuous data as median (25th, 75th %tile)
- c. Run comparisons between baseline and follow-up time points
 - i. Comparisons involving two categorical variables will be made using Fisher's exact test
 - ii. Comparisons involving a continuous variable and a categorical variable will be made using Wilcoxon Rank Sum test or Kruskal Wallis test

b) Worker Survey

- a. Outcome variable of interest
 - i. Opioid misuse- Participant responded yes to one of the following two questions:
 - 1. Did you use the pain medication more than prescribed, or for a longer period than prescribed? [pnmed_longer]x
 - 2. Have you used prescription pain medications that were prescribed to someone else? [pnmed_othersrx]x
 - b. Compute the change at 6 months post-intervention (change of opioid misusep) of group-level data collected from groups of health

All endpoints are independent outcomes.

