9.4.3 ANALYSIS OF THE SECONDARY ENDPOINT(S)

For each secondary endpoint:

Worker Survey

- a) Proportion of workers with lost time. Responded yes to one of the questions below:
 - a. Please refer to the last 12 months for the following questions: Did you miss any days of work because of your pain or discomfort? [missday_pn]x
 - b. In the past 12 months, have you gone to work intoxicated, high, or recovering from the night before? [missday_intox] [*possible reduced productivity]x
- b) Proportion of workers who are willing to seek help. Responded yes to one of the questions below:

Through their workplace:

- a. If I was struggling with a substance use problem... I would be willing to seek help from my supervisor or someone in human resources [help_sup_hr]x
- b. If I was struggling with a substance use problem... I would be willing to seek help from a professional (MAP or behavioral health) [help_prof]x

- c. If I was struggling with a substance use problem... I would be willing to ask a trusted coworker for help [help_coworker]x
- d. Have you attended Alcoholics or narcotics anonymous (AA/NA) group [aa_na_use]x
- e. Have you met with the specialist? [peer_supp_use]x

Seek professional help (employee assistance program or behavioral health)

- f. If benefit is available.... Union sponsored Member assistance program (MAP) [eap]x; Have you used these benefits? Member assistance program (MAP) [eap_use]x
- g. If benefit is available.... Behavioral health (counseling) [behav_health]x; Have you used these benefits? Behavioral health (counseling) [behav_health_use]x

c) Compute the change at 6 months post-intervention (change of lost time and change in willingness to seek help) of group-level data collected from groups of health fund members.

All endpoints are independent outcomes.

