Have you had trouble carrying out normal activities (e.g. job, home, hobbies) because of this trouble in your arms, back, or legs?

- Yes
- No

Have you seen a doctor for this painful condition?

- Yes
- No

Did you miss any days of work because of your pain or discomfort?

- Yes
- No

Have you taken any over-the-counter medications to manage your pain?

- Yes
- No

Have you been prescribed (by a doctor) any pain medication? CHECK ALL THAT APPLY:

- Vicodin
- OxyContin
- Tylenol 3 with codeine
- Percocet
- Darvocet
- Morphine
- Hydrocodone
- Oxycodone
- Other
- I have not been prescribed pain medication.

Did you use the pain medication?

- Yes
- No

Are you currently using this prescription pain medication?

- Yes
- No

Did you use the pain medication more than prescribed, or for a longer period than prescribed?	 Yes  No
Did you use the pain medication for symptoms other than pain, such as to help you sleep, to improve your mood, or to relieve stress?	 Yes  No
Have you used prescription pain medications that were prescribed to someone else?	 Yes  No
In the past 12 months, have you gone to work intoxicated , high, or recovering from the night before?	 Yes  No
In the past 12 months, have you used illicit (illegal) drugs to relieve pain when unable to get pain medications?	 Yes  No

Does your union have any of the following policies related to substance use?

Mandatory drug testing
 Yes
 No
 I don't know

Employee with failed drug tests are given medical treatment/counseling.
 Yes
 No
 I don't know

Does your employer have any of the following policies related to substance use?

	Yes	No	I don't know
Mandatory drug testing			
Safety sensitive jobs (drive equipment, work from heights)			
Light duty work available			
Employee termination for failed drug tests			
Employee given second chance			
		to work if failed drug test	
Naloxone kits are available in			
		the workplace	

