3. Chronic MSD or recurring acute injuries
4. Other diagnoses

- v. Opioid utilization. Number of workers with:
 1. At least one opioid fill
 2. Ever days supply > 7
 3. Ever MME/day > 50
 4. Ever MME/day > 90
 5. Overlapping Rx
 6. Chronic use (>60 day supply in 90-day period)
 7. Multiple Rx on the same day, same provider
 8. Multiple Rx on the same day, different providers
 9. Misuse
- vi. OUD
 1. N by source (diagnosis, MAT fill, both)

- h. Medical claim/opioid linked data
 - i. Distribution of opioid fills by diagnosis, as captured on linked claim

- b) Worker Surveys
 - a. Worker surveys will be distributed to all members of each health fund at start of project, to collect a sample of 300 surveys. We will collect another sample of 300 surveys after 6 months.
 - b. We will examine the serial cross sectional data (baseline & 6mos) by comparing sample characteristics.
 - Age, x
 - gender, x
 - race, x
 - hisp, x
 - unionbenefits, x
 - employstatus, x
 - time_construction, x
 - months_construction, x
 - constype;x
 - c. We will examine the items related to each of the three outcomes of interest
 - i. Opioid misuse- A “yes” response to either of the following two items:
 1. Did you use the pain medication more than prescribed, or for a longer period than prescribed? [pnmed_longer]x
 2. Have you used prescription pain medications that were prescribed to someone else? [pnmed_othersrx]x
 - ii. Proportion of workers with lost time- A “yes” response to either of the following two items:

1. Please refer to the last 12 months for the following questions: Did you miss any days of work because of your pain or discomfort? [missday_pn]x
2. In the past 12 months, have you gone to work intoxicated, high, or recovering from the night before? [missday_intox] [*possible reduced productivity]x
- iii. Proportion of workers who are willing to seek help
 - 1) their workplace
 1. If I was struggling with a substance use problem... I would be willing to seek help from my supervisor or someone in human resources [help_sup_hr]x
 2. If I was struggling with a substance use problem... I would be willing to seek help from a professional (MAP or behavioral health) [help_prof]x
 3. If I was struggling with a substance use problem... I would be willing to ask a trusted coworker for help [help_coworker]x
 4. Have you attended Alcoholics or narcotics anonymous (AA/NA) group [aa_na_use]x
 5. Have you met with the specialist? [peer_supp_use]x

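### The survey misuse endpoint states no recall period: if it is 12 months, about half of the 6-month measure predates the intervention; if it is open-ended, the proportion can hardly fall.

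*Combined protocol and SAP*

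**What the plan says.** Section 9.4.2 b defines survey misuse as a yes to either "Did you use the pain medication more than prescribed, or for a longer period than prescribed? [pnmed_longer]x" or "Have you used prescription pain medications that were prescribed to someone else? [pnmed_othersrx]x". The annex on data management of claims and worker surveys repeats the definition. Neither place adds a time window, and in the printed survey (additional document B) neither item has one of its own.

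Other items do have a window. Section 9.4.3 and the annex give the missed-days item with a lead-in: "Please refer to the last 12 months for the following questions: Did you miss any days of work because of your pain or discomfort". In the survey, the question straight after the second misuse item begins "In the past 12 months, have you gone to work", and the next one, on illicit drugs, restates the same period.

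On timing, 9.1 says: "We will assess change in opioid misuse at 6 months following delivery of the intervention". Section 9.4.1 places the two waves before implementation and 6 months after its start, and allows that a change between them may reflect the intervention. The Schedule of Activities puts the second survey at Day 180±30. Sections 9.1 and 9.2 say that the data will be used to compute power for a later trial.

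**The concern.** A change score can be interpreted only if the follow-up measure describes time after the intervention began. Here the plan does not say what period the misuse items cover. The two periods that the documents allow, 12 months or no limit, are both longer than the 6 months being assessed. Misuse from before Day 1 is then counted again at follow-up, and the change shrinks toward zero.

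This is one of the two primary endpoints, and the only planned endpoint built on self-reported misuse. The claims endpoint cannot register use of someone else's medication. A base rate with an unknown window, or a change diluted by half, would pass directly into the planning of the future trial.

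**Working it through.** **Plan's own figure.** 3 funds × 300 surveys × 2 waves = 1,800, and × 3 waves = 2,700; both match 9.2. (The total of 900 for two waves in 5.5 matches one wave only, which is a separate matter.) I use 900 per wave. The plan gives no planning prevalence, detectable change or test, so the sizes below are illustrations.

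**Reading A: the 12-month lead-in covers both items.** Share of the window before Day 1 = (365 − survey day)/365:

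- Day 150: 215/365 = 59%
- Day 180: 185/365 = 51%
- Day 210: 155/365 = 42%

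Dilution under a constant misuse rate. Let L = −ln(1 − baseline) and let r be the true cut in the rate from Day 1. With half the window on each side of Day 1, the follow-up proportion is 1 − exp[−(0.5L + 0.5L(1 − r))].

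Illustrative baseline: 34% past-year prescription opioid use × 17% misuse among users (section 2.2, general population) = 5.8%, so L = 0.0595.

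- r = 50%: 1 − exp(−0.75 × 0.0595) = 4.4%, a fall of 1.4 points, or 24% relative.
- r = 100%: 1 − exp(−0.5 × 0.0595) = 2.9%, a fall of 2.8 points, or 49% relative.
- With baselines of 3% to 10%, a 50% cut appears as 24-25%.

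The 95% half-width for the change is 1.96 × √(2 × 0.0578 × 0.9422/900) = 2.2 points, larger than the 1.4 points visible after a true halving.

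Two features make these figures optimistic. They start the effect on Day 1, although the fund must first obtain approval from its board of trustees (6.1.1). They also assume a constant rate: if the same workers misuse all year, those who stopped on Day 1 still answer yes at Day 180, and the visible fall can be near zero even with full cessation.

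**Reading B: open-ended items.** With fixed membership, past misuse stays positive, so the proportion can stay level or rise but not fall. Turnover can move it slightly. Assume 5% turnover, entrants with half the prevalence, and prevalence 10-30%: the fall is 0.05 × prevalence/2 = 0.25 to 0.75 points, none of it an intervention effect.

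**What a shorter window would do.** Same model, baseline 5.8% over 12 months, true cut 50%, shorter windows taken as wholly after Day 1:

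| Window | Baseline | Follow-up | Relative fall | Fall / 95% half-width |
|---|---|---|---|---|
| 12 months | 5.8% | 4.4% | 24% | 1.41/2.16 = 0.65 |
| 6 months | 2.9% | 1.5% | 50% | 1.46/1.56 = 0.93 |
| 3 months | 1.5% | 0.7% | 50% | 0.74/1.12 = 0.66 |

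The baselines are 1 − exp(−L/2) and 1 − exp(−L/4). A 6-month window (about 183 days) asked at Day 150 still reaches 183 − 150 = 33 days before Day 1. A 3-month window (about 91 days) asked at Day 150 begins near Day 59. In this model the 3-month window recovers the size of the effect but adds no precision over the diluted 12-month measure.

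**The case against.** A reader might infer that the items measure lifetime misuse, that a yes can never revert, and that no fall could ever be seen. The documents do not support that.

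- The lead-in is plural: "Please refer to the last 12 months for the following questions". In the survey the missed-days item is printed without it and after two other pain questions, so the lead-in seems to stand earlier and to govern several items. The survey pages before that point are not in the text available for review. Both misuse items come later in the same run of pain and medication questions. The items that restate 12 months change topic, so the restatement does not prove that the lead-in had lapsed.
- The first misuse item refers back to the prescribed medication asked about just before it, and takes whatever window those questions have.
- The waves are unlinked cross-sections. A statement about one person's answer does not fix the group proportion, which also moves with turnover and response.
- Under 12 months the fall is diluted, not abolished.

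It can also be said that this is a feasibility study: section 9.1 plans no formal testing, and section 3 says the study is not powered for change and defines success by recruitment and data collection. Nothing says that an unchanged proportion would be reported as no effect.

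All of this stands, and it rules out the lifetime claim. It does not remove the defect: the window is unstated, neither available reading fits a 6-month change, and that change is meant to inform a later trial. A 12-month survey would largely solve the problem under a 12-month lead-in, but 9.2 makes it conditional on time, and the Schedule of Activities lists surveys only at baseline and Day 180.

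**Conclusion.** The point holds in this form: the survey primary endpoint has no stated recall period, and under either reading the 6-month change understates an effect on misuse. With a 12-month window, 42-59% of the follow-up period predates Day 1; a true halving shows as about 24% and complete cessation as about 49%. With an open-ended window, a fall could come only from turnover or from who responds.

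The overlap percentages follow from the schedule alone. The dilution figures rest on a constant misuse rate and an effect from Day 1. The point sizes also rest on the 5.8% illustration, which is not a planning value. Which reading applies cannot be settled from the available text. For a descriptive feasibility study the consequence is moderate, and it falls mainly on the planning of the next trial.

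**What to change.** Put one explicit window, no longer than the follow-up interval, into both misuse items at both waves, and state it in 9.4.2 b and the annex. The past 3 months would lie wholly after Day 1 even at Day 150.

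Section 8.1 describes the survey in the past tense, so baseline may already be fielded. In that case:

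- keep the same wording at both waves;
- report the endpoint with the window actually asked, and do not label it as ever-misuse unless the survey shows that no lead-in applied;
- state that the 6-month change includes pre-intervention time and is not to be read as the intervention effect;
- if the lead-in is 12 months, treat the optional 12-month survey as the first wave essentially free of overlap (at Day 360, 5/365 = 1% of the window; at Day 330, 35/365 = 10%).

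The cost is a few words in two REDCap items and a sentence in each of two places. The downside is lower prevalence and wider relative precision. Under the constant-rate illustration, the relative standard error of one wave's proportion, √((1 − p)/(900p)), rises from 13% at p = 5.8% to 27% at p = 1.5%.

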9.4.3 ANALYSIS OF THE SECONDARY ENDPOINT(S)

For each secondary endpoint:

Worker Survey

- a) Proportion of workers with lost time. Responded yes to one of the questions below:
 - a. Please refer to the last 12 months for the following questions: Did you miss any days of work because of your pain or discomfort? [missday_pn]x
 - b. In the past 12 months, have you gone to work intoxicated, high, or recovering from the night before? [missday_intox] [*possible reduced productivity]x
- b) Proportion of workers who are willing to seek help. Responded yes to one of the questions below:

Through their workplace:

- a. If I was struggling with a substance use problem... I would be willing to seek help from my supervisor or someone in human resources [help_sup_hr]x
- b. If I was struggling with a substance use problem... I would be willing to seek help from a professional (MAP or behavioral health) [help_prof]x

- c. If I was struggling with a substance use problem... I would be willing to ask a trusted coworker for help [help_coworker]x
- d. Have you attended Alcoholics or narcotics anonymous (AA/NA) group [aa_na_use]x
- e. Have you met with the specialist? [peer_supp_use]x

Seek professional help (employee assistance program or behavioral health)

- f. If benefit is available.... Union sponsored Member assistance program (MAP) [eap]x; Have you used these benefits? Member assistance program (MAP) [eap_use]x
- g. If benefit is available.... Behavioral health (counseling) [behav_health]x; Have you used these benefits? Behavioral health (counseling) [behav_health_use]x

c) Compute the change at 6 months post-intervention (change of lost time and change in willingness to seek help) of group-level data collected from groups of health fund members.

All endpoints are independent outcomes.

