1 PROTOCOL SUMMARY

Title:	Improving Health and Employment Outcomes Through Workplace Opioid Policies
Grant Number:	1R34DA050044-01
Study Description:	We will implement the intervention in three local union health funds, evaluate the implementation using the RE-AIM framework, and collect the data needed to measure effectiveness of the workplace opioid guidelines. We will measure a) the health fund's adoption of policies and programs; b) opioid prescriptions, chronic opioid use, and OUD in health claims and pharmacy data; c) changes in knowledge, attitudes, and beliefs of employers, health fund administrators, and employees; and d) employee participation in employee assistance programs and healthcare recovery services.
Objectives*:	The overall aim is to evaluate the feasibility of implementing workplace opioid guidelines in the construction trades; define and collect measures of implementation and effectiveness. The primary objective is to evaluate a change in opioid misuse and opioid use disorder from medical and pharmacy claims, and worker surveys following a change in policies and programs within health funds. The secondary objective is to evaluate a change in lost time and willingness to seek help among workers who are struggling with opioid misuse or substance use problems on worker surveys.
Endpoints*:	The primary endpoints are a) the change in the proportion of workers with opioid misuse, opioid use disorder and opioid overdose: administrative data and b) in the proportion of workers with opioid misuse: worker surveys from baseline to 6-months. The secondary endpoints are a) the change in the proportion of workers with lost time: worker surveys and b) the proportion of workers who are willing to seek help: worker surveys from baseline to 6-months.
Study Population:	Participants will be members of three participating union health funds. We anticipate these unions will have 33300 members enrolled between 2019-2023, which is the period of data used for the trial. All union members of the participating health funds will be enrolled in the study. We expect the demographics of the participants will reflect the demographics of the membership, which is approximately 8% female, and 90% Caucasian. All participants will be located within the geographical region of the union membership.
Phase* or Stage:	This is a feasibility trial.

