of national data have shown that rates of opioid overdose deaths are significantly higher among workers employed in industries and occupations with higher rates of work-related injuries and illnesses.³² Second, construction work is often intermittent, and workers are usually paid only for time worked. Analysis of data across all occupations showed that opioid death rates are significantly higher among workers in occupations with lower availability of paid sick leave and lower job security, suggesting that the need to return to work soon after an injury or to work while in pain may contribute to high rates of opioid-related overdose deaths among workers in construction and other industries.³² Third, in addition to having a higher chance of receiving an opioid prescription, construction workers have higher rates of alcohol and tobacco use than the general population,³⁵ putting them at higher risk of developing OUD after initiation of opioids. National organizations of construction unions and employers are becoming aware of this issue and have a strong incentive to address this crisis.^{36, 37} Importantly, the structure of health benefits and employment of union construction workers makes this group well suited to test policy and guideline changes. In collaboration with construction industry leaders and union health plans, in **Aim 2** we will further characterize the opioid problem in construction and create guidelines on opioid use by adapting best-practice healthcare and employment policies to the unique needs of the construction industry.

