4.3 JUSTIFICATION FOR INTERVENTION

The construction industry has one of the highest overdose rates of any industry, with the majority of those overdoses from opioids. The industry has one of the highest injury rates with many workers suffering from chronic disorders incurred from work activities. Prescription opioids have been prescribed to treat these chronic disorders. The union health fund provides the health benefits and health programs for the union members. There is a need to provide union health funds with guidance on policies, programs and benefits that may help prevent initial use of prescription opioids and treatment for members with opioid misuse and opioid use disorder. The Workplace Guidelines to Prevent Opioid and Substance Abuse for the Construction Trades are evidence-based guidelines designed for use by the construction industry. The guidelines are intended to be used by construction organizations to assess their need, and provide guidance and off the shelf resources that may be tailored for use by the organization. The overall goal of the guidelines are to reduce the incidence of opioid misuse and opioid use disorder, missed days of work due to opioid use, and increase members willingness to seek treatment if they need help.

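### Neither of the two items in the lost-time endpoint measures opioid-related absence, which is the stated goal, and a change in the pain-absence item has no clear direction

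*Combined protocol and SAP*

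**What the plan says.** Section 4.3 lists among the goals of the guidelines a reduction in "missed days of work due to opioid use". The secondary objective in the Protocol Summary is to "evaluate a change in lost time and willingness to seek help among workers who are struggling with opioid misuse or substance use problems".

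The endpoint is defined in 9.4.3 a: "Proportion of workers with lost time. Responded yes to one of the questions below". The two items are:

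- `missday_pn`, with a 12-month recall: "Did you miss any days of work because of your pain or discomfort"
- `missday_intox`: "In the past 12 months, have you gone to work intoxicated, high, or recovering from the night before". The plan annotates this one as a possible sign of lower productivity.

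The data management appendix in 10.2 (Worker Surveys, item c.ii) repeats the same either/or rule. In the worker survey itself, `missday_pn` comes shortly after a question on difficulty with normal activities "because of this trouble in your arms, back, or legs".

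**The concern.** An endpoint should measure the thing the objective names. Here the goal attributes lost work to opioid use, while the only absence item attributes it to pain. The other item is about being at work, not away from it. The plan could be followed exactly and still not say whether opioid-related absence changed.

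The pain item also lacks a clear benefit direction. Section 2.2 says that the need to return early after an injury or "to work while in pain may contribute to high rates of opioid-related overdose deaths". On that reasoning, a worker who stays home instead of working in pain may be doing better, yet answers yes to `missday_pn`. Section 2.2 also describes a state workers' compensation programme in which tighter authorisation of opioids was followed by improved lost-work patterns, which is a reason for the item to fall.

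Section 9.4.1 says that a change in survey proportions may be due to the intervention, so the number is likely to be interpreted. Sections 9.1 and 9.2 say that the data will inform power calculations for a future trial, so a mis-targeted endpoint could carry over.

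**Working it through.** The plan gives no lost-time rate, effect size or power calculation for this endpoint, so there is no figure to reproduce. The check compares the definitions and then works through the scoring rule.

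**1. Goal against measure**

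| | Absence from work? | Attributed to opioids? | Population |
|---|---|---|---|
| Goal in 4.3 | Yes | Yes | Members |
| Secondary objective, Protocol Summary | Lost time | Opioid misuse or substance use problems | Workers with those problems |
| `missday_pn` | Yes | No, pain | All respondents |
| `missday_intox` | No, impaired attendance | No, any substance | All respondents |

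No item is both an absence and attributed to opioid use. Section 9.4.3 and the appendix list every item that feeds the endpoint, so this holds whatever else the survey contains. Work hours are requested in the claims variable list, and 2.3.2 names them as a source of employment outcomes. They feed no endpoint in 9.4 and would not give the reason for an absence.

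**2. Scoring rule**

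Lost time = 1 if `missday_pn` = yes or `missday_intox` = yes, otherwise 0.

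| Change in behaviour | `missday_pn` | `missday_intox` | Score |
|---|---|---|---|
| Stops working in pain, stays home; not impaired at work | no → yes | no → no | 0 → 1 |
| Same, but reports impairment at work both times | no → yes | yes → yes | 1 → 1 |
| Same, and stops being impaired at work | no → yes | yes → no | 1 → 1 |
| Stops missing days because of opioid use; no pain absence, no impairment at work | no → no | no → no | 0 → 0 |

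The first row is scored as worse. The second and third rows do not move. In the fourth row, the outcome named in 4.3 improves and the endpoint does not register it.

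Let s be the share of workers who make the switch in the first two rows, and q the share of those who answer yes to `missday_intox` both times. The composite then changes by s × (1 − q): s if q = 0, and zero if q = 1. The documents give neither s nor q, so no value is attached.

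**3. Recall window**

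Both items look back 12 months, and the follow-up survey is at 6 months. About 12 − 6 = 6 of the 12 months, or half the window, precede the intervention. That blurs a change in either direction.

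**The case against.** **Low stakes.** The endpoint is secondary, 9.1 rules out formal hypothesis testing, and section 3 defines success as recruiting three funds and collecting the measures. Section 9.4.3 asks only for the change to be computed. The explicit reference to a reduction in 9.4.1 concerns the claims outcomes, not the surveys. All of this stands and limits the weight of the point. It does not supply a measure of the goal.

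**Wording of the objective.** The phrase about struggling workers in the Protocol Summary could be read as qualifying only willingness to seek help. The mismatch with 4.3 would remain.

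**Text not available.** The opening part of the survey was not in the text available, so it cannot be said that no question anywhere asks about opioid-related absence. It can be said that none feeds this endpoint.

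**Stronger readings the documents do not support.**

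- A reader might infer that any worker who stays home in place of working in pain counts as a worse result. Under the either/or rule, that is so only for those who answer no to `missday_intox`.
- A reader might infer that more pain-related absence would cancel a real fall in opioid-related absence within the endpoint. Opioid-related absence is not measured, so its fall does not enter the score unless workers report that absence as pain. The documents do not suggest that they do.
- A reader might infer that pain-related absence will rise if the programme works. The evidence on prescribing controls in 2.2 supports a fall at least as well. The guidelines also ask funds to cover non-opioid pain care, not only to limit opioid supply.

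**Conclusion.** The concern holds as a mismatch between goal and measure. Neither of the two items feeding the lost-time endpoint captures days missed because of opioid use, and the rule is applied to all respondents. A change in the composite therefore cannot be read as success or failure on the goal in 4.3. A change in `missday_pn` alone is also ambiguous, because section 2.2 gives reasons for it to move either way.

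The conclusion rests only on the definitions in 4.3, the Protocol Summary, 9.4.3 and the appendix. No size in percentage points is claimed: any such figure would depend on assumed rates of pain absence, switching and impairment at work that the documents do not contain. The change should be made, but the point does not threaten the feasibility aims.

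**What to change.** In 9.4.3 a and the matching appendix text:

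1. Replace the composite with two separately reported items: `missday_pn` as *pain-related absence* and `missday_intox` as *impaired at work*. State that a change in `missday_pn` will not be read as success or failure on the goal in 4.3.
2. At each wave, tabulate both items by survey-reported misuse (`pnmed_longer` or `pnmed_othersrx`) and by current use of prescription pain medication. All of these are already asked. Note that the medication list includes an *Other* option and so is not specific to opioids.
3. Add one yes/no item with the same stated 12-month window, for example: *In the past 12 months, did you miss any days of work because of your use of opioids or other substances, not counting leave for treatment?* Treatment leave is excluded because the guidelines encourage it.
4. Section 8.1 describes baseline collection in the past tense. If baseline is still open, ask the new item at both waves. If it is closed, ask it at the remaining wave and in the future trial's instrument.

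**Cost.** Steps 1 and 2 need only wording and tables. Step 3 adds one question to a survey of about 10 minutes. The new item will have a lower rate, so its relative change will be less precise, and it shares the overlap of the recall window with the pre-intervention period. With a target of 300 surveys per fund per wave, subgroup counts will be small. If baseline is closed, the new item gives no pre-post change in this trial.
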